7.6.3 Body weight

Body weight (kg) will be measured at Visits 2 and 8, and Visit 9 (or at discontinuation of the treatment period or tapering period). The date and result of measurement will be recorded in the CRF. The principal investigator or sub-investigator will judge whether any abnormal change from baseline (Visit 2) is clinically significant (refer to Section 7.6.7.7) and will record any changes judged to be clinically significant as adverse events.

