7.6.6 Laboratory tests

7.6.6.1 Laboratory test items

At Visits 1, 5, 8 and 9, or at discontinuation of the treatment period or tapering period, blood samples will be collected for laboratory tests, the volumes being 2 mL for hematology tests, and 8 and 5 mL for blood chemistry tests, at Visit 1 and other visits, respectively; and urine samples will also be collected. The samples will then be sent to the clinical laboratory facility specified in Section 7.6.6.2. Details of the collection, handling, storage, and shipment of samples are stipulated in a separate document.

The principal investigator or sub-investigator will judge whether any abnormal change from baseline (Visit 1) is clinically significant (see Section 7.6.7.7) and will record any changes judged to be clinically significant as adverse events. The sample collection dates will be recorded in the CRF for each sample type (blood or urine).

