### 5.3 Safety-analysis set

This set comprises all randomized subjects to whom the study drug has been administered at least once. Analysis of this set will be performed with subjects actually administered the study drug, rather than allocated group.

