### 6.3 Assessments, observations and tests: Permitted timing and handling in statistical analyses

In principle, data obtained at the time-points shown in the case report forms, and collected in accordance with the performance schedule shown in the study protocol, will be used for the statistical analysis. In the case of data reported at the discontinuation visit, the time-points for use in analyses will be determined on the basis of the permitted ranges in the performance schedule. If there is duplication by data obtained at the scheduled visits and data obtained at the discontinuation tests, the data obtained closest to the scheduled date will be used. If this does not eliminate duplication, data from the scheduled visit will be used. Unscheduled visits will not be included in the time-points for analysis. For the permitted ranges for the observation, test, and evaluation time-points shown in the study protocol, refer to Appendix 2.

For the final evaluation, data obtained at week 7 or at discontinuation of the treatment or tapering period are used, except for CDRS-R and CGI-S scores, for which those obtained at week 6 or at discontinuation of the treatment period are used. However, if none of the above data are available, the latest data among reported data collected at scheduled visits are used for the final evaluation.

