### 6.4 Handling of missing data

In principle, missing data will not be imputed. If missing data for CDRS-R total scores 6 weeks after initial administration are nevertheless imputed for the secondary efficacy analyses, this will be performed by the last observation carried forward (LOCF) method, baseline observation carried forward (BOCF) method, and modified BOCF method.

If missing data imputation is performed by the LOCF method, the measurements used as substitutes will be those obtained at the latest scheduled evaluation time-points (Visits 3, 4, 5, 6 and 7) before the missing-data time-points.

If missing data imputation is performed by the BOCF method, the baseline data will be used as substitutes.

The modified BOCF method is defined as follows:

- With subjects withdrawn from the study due to adverse events and/or insufficient efficacy, imputation will be by the BOCF method.
- With subjects withdrawn from the study for any reason other than the above, imputation will be by the LOCF method.

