### 6.5 Baseline

Data obtained before initiation of study drug administration (Visit 2) will be used as baseline data, unless otherwise specified. As with laboratory test results, if data from Visit 2 are missing, data from Visit 1 (screening period) will be used as baseline data.

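### SAP 6.3 lets a pre-dose value stand as the safety final evaluation, with a change of exactly zero, although protocol 8.11.2 and 8.11.3 summarize only measurements scheduled after randomization

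*SAP*

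**What the plan says.** For the safety measures, SAP 6.3 says that in the final evaluation "data obtained at week 7 or at discontinuation of the treatment or tapering period are used, except for CDRS-R and CGI-S scores". If neither source exists, "if none of the above data are available, the latest data among reported data collected at scheduled visits are used for the final evaluation". The same section keeps unscheduled visits out of the analysis time-points.

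SAP 6.5 defines baseline: "Data obtained before initiation of study drug administration (Visit 2) will be used as baseline data", and "if data from Visit 2 are missing, data from Visit 1 (screening period) will be used as baseline data". Laboratory tests fall under the second rule, since they are taken at Visit 1 and not at Visit 2; SAP 10.3 labels the screening period as their baseline.

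SAP 10.2 (blood pressure, pulse, weight) and SAP 10.3 (laboratory tests) then summarize observed values and changes from baseline at the final evaluation, by group. The safety-analysis set is "all randomized subjects to whom the study drug has been administered at least once", so a subject with no post-dose measurement belongs to it.

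The protocol schedules are sparse for two measures. For weight: "Body weight (kg) will be measured at Visits 2 and 8, and Visit 9 (or at discontinuation of the treatment period or tapering period"). For laboratory tests: "At Visits 1, 5, 8 and 9, or at discontinuation of the treatment period or tapering period, blood samples will be collected". Blood pressure and pulse are taken at every visit from 1 to 9 (protocol 7.6.4), Visit 6 being optional.

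Protocol 8.11.2 and 8.11.3 restrict the corresponding summaries to measurements scheduled after randomization.

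**The concern.** The fallback contains no post-dose condition, and both pre-dose visits are scheduled visits in SAP Appendices 1 and 2. Where the last scheduled value is the baseline, the rule reports that baseline as an end-of-study result and its change from itself, zero, as an observed change. SAP 10.2 and 10.3 describe this column as week 7 or discontinuation, so a reader of the tables would not know that it could hold pre-dose values.

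The SAP sets the limit elsewhere. For LOCF of the CDRS-R, SAP 6.4 uses the "latest scheduled evaluation time-points (Visits 3, 4, 5, 6 and 7) before the missing-data time-points", all of them post-dose. The safety fallback in SAP 6.3 has no such list.

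At stake is the accuracy of one descriptive column: each zero pulls that arm's mean change toward no change. There is also an unexplained difference between the SAP and the protocol.

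**Working it through.** **1. Who falls through.** In every case the subject has been dosed and has no Visit 9, treatment-discontinuation or tapering-discontinuation value. The change is then zero under this further condition:

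| Measure | Baseline | First scheduled post-dose value | Further condition for a zero |
|---|---|---|---|
| Body weight | Visit 2 | Visit 8 | no Visit 8 weight |
| Laboratory tests | Visit 1 | Visit 5 | no sample at Visit 5 or later |
| Blood pressure, pulse | Visit 2 | Visit 3 | no measurement at Visit 3 or later |

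Reach is widest for weight, where any withdrawal before Visit 8 can qualify and not only an early one. It is narrowest for blood pressure and pulse.

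**2. Can the discontinuation values be absent?** Yes. Protocol 4.5 asks for these assessments only as far as possible. Protocol 7.8 gives the discontinuation visit a window of 0 to +3 days and treats data outside the window as missing for that visit. Protocol 5.2 gives no taper after discontinuation in week 1 and allows the taper to be omitted in some other cases.

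**3. Arm size.** The plan's own figure reproduces. With difference 5.9, SD 12.0, two-sided alpha 0.05 and 80% power, the two-sample t-test needs n = 65.9, so 66 per group (power 80.05%). Then 66/0.9 = 73.3, so 74 per group and 148 in total.

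**4. Effect on the mean.** Let μ be the mean change among subjects with a post-dose value. With k zeros among 74, the reported mean is (74 - k)μ/74 = μ(1 - k/74). The documents do not give k, so it is an assumption:

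- k = 1: 1 - 1/74 = 0.986
- k = 2: 1 - 2/74 = 0.973
- k = 4: 1 - 4/74 = 0.946
- k = 7: 1 - 7/74 = 0.905

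The last line is the bound: 10% of 74 is 7.4, taken as 7, and every one of those dropouts would have to lack every post-dose value.

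As an illustration, suppose a mean weight change of 0.5 to 1.0 kg (not in the documents). Two zeros then move the mean by 0.5 × 2/74 = 0.01 kg to 1.0 × 2/74 = 0.03 kg.

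**5. Effect on the SD.** With f = k/74, the variance is (1 - f)σ² + f(1 - f)μ². Subtracting σ² leaves f[(1 - f)μ² - σ²]. The SD therefore falls only if (1 - f)μ² < σ², that is, when the mean change is smaller than roughly one SD. Otherwise the zeros widen it.

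**6. What is not touched.** ECG (SAP 10.4) and C-SSRS (SAP 10.5) have their own categories for subjects not observed or not assessed after dosing. The week-by-week summaries use values at those weeks. CDRS-R is largely protected, because the FAS requires a post-dose CDRS-R total score. Adverse-event analyses and the primary MMRM do not use the final evaluation.

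**The case against.** The strongest reply is that the protocol already settles the matter. Protocol 8.11.2 and 8.11.3 confine these summaries to measurements scheduled after randomization, SAP 1 presents itself as making protocol Section 8 concrete, and protocol 8.1 requires a stated reason for any change, of which the SAP gives none. SAP 10.2 and 10.3 list baseline and final evaluation as separate time-points, and SAP 6.4 says that missing data are in principle not imputed. The separate output plan, which is not available here, might also settle it. This is good evidence of intent. It does not change what SAP 6.3 instructs: neither that section nor 10.2 or 10.3 carries the limit into the fallback, and a programmer following the text would reach the baseline.

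The second reply, that few subjects can be affected, largely stands. Weight and laboratory tests are called for at treatment discontinuation and again at Visit 9 or tapering discontinuation, so a zero needs both to be missing as well as the earlier scheduled value.

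A reader might infer that the zeros come mainly from children who did badly on drug, so that harm is hidden. The documents do not show this. Protocol 4.5 follows up subjects withdrawn for adverse events, and Appendix 2 asks for repeat tests after liver abnormalities. Refusal or loss to follow-up would explain absent data equally well.

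**Conclusion.** The point holds as a wording fault with a small effect. Applied literally, SAP 6.3 and 6.5 give a dosed subject without any post-dose value a final-evaluation change of exactly zero, and this conflicts with protocol 8.11.2 and 8.11.3.

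Its size depends on an unknown count: one to four subjects per arm, an assumed range, would shrink an arm's mean change by about 1% to 5%. A reader might take the shrinkage of about 9.5% at seven subjects as the expected effect. It is only a bound, and it is relevant mainly to weight, since fewer dropouts can qualify for laboratory tests and fewer still for blood pressure and pulse. Nor may one infer that variability is always understated, because the direction depends on the ratio of mean to SD.

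The consequence is confined to the descriptive final-evaluation summaries of weight, vital signs and laboratory tests. The sample size and the primary analysis are unaffected.

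**What to change.** Reword the fallback in SAP 6.3 along these lines: *the latest data collected at scheduled visits after the first dose of study drug are used; subjects with no post-dose value are not included in the final evaluation.* This brings it into line with protocol 8.11.2 and 8.11.3, and it needs no change to the schedule or to data collection.

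The cost is a few words and a slightly smaller n at the final evaluation, which should be shown in the tables.

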### 6.4 Handling of missing data

In principle, missing data will not be imputed. If missing data for CDRS-R total scores 6 weeks after initial administration are nevertheless imputed for the secondary efficacy analyses, this will be performed by the last observation carried forward (LOCF) method, baseline observation carried forward (BOCF) method, and modified BOCF method.

If missing data imputation is performed by the LOCF method, the measurements used as substitutes will be those obtained at the latest scheduled evaluation time-points (Visits 3, 4, 5, 6 and 7) before the missing-data time-points.

If missing data imputation is performed by the BOCF method, the baseline data will be used as substitutes.

The modified BOCF method is defined as follows:

- With subjects withdrawn from the study due to adverse events and/or insufficient efficacy, imputation will be by the BOCF method.
- With subjects withdrawn from the study for any reason other than the above, imputation will be by the LOCF method.

### 6.5 Baseline

Data obtained before initiation of study drug administration (Visit 2) will be used as baseline data, unless otherwise specified. As with laboratory test results, if data from Visit 2 are missing, data from Visit 1 (screening period) will be used as baseline data.

## 7. Subject composition and backgrounds

### 7.1 Disposition of patients

Among registered subjects, the number who complete the treatment period and the number of withdrawals are calculated for each treatment group, and in the case of the withdrawals the disposition of the reasons for discontinuation is shown. Among subjects transferred to the tapering period, the number who complete the tapering period and the number of withdrawals are calculated, and the disposition of the reasons for discontinuation is summarized.

#### 7.1.1 Patient composition in efficacy evaluation

With registered subjects, the numbers included in and excluded from the FAS will be calculated for each treatment group, and the disposition of the reasons for exclusion will be shown. Similar analysis will be performed for the PPS.

#### 7.1.2 Patient composition in safety evaluation

With registered subjects, the numbers of subjects included in and excluded from the safety-analysis set will be calculated for each treatment group, and the disposition of the reasons for exclusion will be shown.

### 7.2 Analysis of demographic factors

With the FAS, for each treatment group, summary statistics will be determined for the following continuous data items; and the frequencies and proportions of subjects in each category will be determined for discrete values:

Data type	Item
Continuous	Age on date of obtaining legal representative's informed consent, age at initial onset of depression, height, body weight, CDRS-R total score baseline value, CDRS-R subscale (mood, somatic, subjective, behavioral) baseline values, CGI-S score baseline value
Discrete	Sex (male, female), ethnicity, race, age on date of obtaining legal representative's informed consent (<12, ≥12), depressive episode ordinal number (first time, second time, third to seventh time, eighth time or more, not known), duration of current depressive episode (0 to 2 weeks, 2 to 4 weeks, 4 to 8 weeks, more than 8 weeks, not known), CDRS-R total score baseline value (up to 60, 61 or more), disease class according to DSM-5 (depression, persistent depressive disorder), hospitalization status category (hospitalized, out-patient), medical and surgical history (present, absent), complications (present, absent), previous drug treatment (present, absent), previous therapy (present, absent)

The dispositions of medical and surgical history, complications, previous drug treatment, and previous therapy are shown for each treatment group. Drugs used previously will be coded for using the WHO Drug Dictionary, and summarized on the basis of consistently selected noncommercial names.

## 8. Treatment course and compliance

### 8.1 Compliance

#### 8.1.1 Duration of administration and total dose

The following analyses will be performed with the safety-analysis set:

- 1) Summary statistics for study drug administration duration will be calculated for each treatment group. Administration duration is defined as follows:

Administration duration (days) = (administration completion date) – (administration initiation date) + 1.

In addition, times (days) will be converted to week units, and the distributions in the following categories will be summarized: less than 1 week; 1 to 2 weeks; 2 to 6 weeks; and more than 6 weeks.

- 2) Summary statistics will be calculated for the total dose of study drug in the duloxetine group.
- 3) With the duloxetine group, for the maximum and final doses during the treatment period, distribution in the following categories will be summarized: 20 mg, 40 mg, and 60 mg.

#### 8.1.2 Compliance rate

In the safety-analysis set, summary statistics for compliance rate during the treatment period will be calculated for each treatment group. Distribution in the following categories will be summarized: less than 70%, and 70% or more. Compliance rate is defined as follows:

$$\text{Compliance rate [\%]} = \frac{\{Total\ Prescription - 20 \times (Total\ number\ of\ unfilled\ capsules) - Total\ mis\ prescription\}}{(Total\ Prescription)} \times 100$$

## 8.2 Concomitant treatment

The following analyses will be performed with the safety-analysis set: Concomitant drugs will be coded for using the WHO Drug Dictionary, and then summarized on the basis of consistently selected noncommercial names.

- 1) The number and proportion of subjects who have taken any concomitant medication at least once during the study period will be calculated. In addition, the disposition of the concomitant medication(s) will be shown. If use of the same concomitant medication has been reported more than once with the same subject, this will be taken to be one concomitant medication.
- 2) The number and proportion of subjects who have had any concomitant therapy at least once during the study period will be calculated. In addition, the disposition will be shown by the name of concomitant therapy. If use of the same concomitant therapy has been reported more than once with the same subject, this will be taken to be one concomitant therapy.

## 9. Efficacy evaluation

Efficacy endpoints and the relevant analytical methods are summarized in Table 1. For the primary

endpoint, CDRS-R total total score, the primary analysis will be by the mixed-effects model repeated measures (MMRM) method, and the secondary analysis will be by analysis of covariance. With the FAS, each endpoint will be analyzed. In addition, with the PPS, the primary analysis of the primary endpoint, change in CDRS-R total total score, will be performed.

Table 1. Summary of endpoints and analysis methods

Endpoints	Analysis method a	Output contents b	Analysis sets c	
			FAS	PPS
Primary	Change in CDRS-R total score	1, 2, 4	○	○ d
Secondary	CDRS-R total score response rate, remission rate	3	○	–
	Change in CDRS-R subscales and item 13 (suicidal ideation)	1	○	–
	Change from baseline in CGI-S score	1	○	–

- a Analysis method 1: MMRM method  
Analysis method 2: Analysis of covariance  
Analysis method 3: Cochran-Mantel-Haenszel test  
Analysis method 4: Tipping-point analysis
- b Output contents 1: Summary statistics  
Output contents 2: Adjusted mean, inter-group difference in adjusted mean and 95% confidence interval, p-value  
Output contents 3: Inter-group difference and 95% confidence interval, p-value  
Output contents 4: Time-course graph for adjusted mean and standard error
- c In the table: ○: performed; –: not performed
- d In the case of the primary analysis of the primary endpoint only, analysis is performed with the PPS.

## 9.1 Primary endpoint

CDRS-R total score is the primary endpoint, and its change from baseline is the primary evaluation index.

### 9.1.1 Primary analysis of primary efficacy endpoint

As the primary analysis, the superiority of duloxetine over placebo will be evaluated in terms of change in CDRS-R total score by week 6 of administration. In detail, all usable data obtained at stipulated time-points after study drug administration will be used, and a linear model (MMRM) will be applied, with change in CDRS-R total score from baseline taken to be a response variable; treatment group, observation time-points, and interaction between treatment group and observation time-points taken to be fixed effects; baseline CDRS-R total score and age (<12, ≥12) taken to be covariates; and an unstructured covariance structure for error variance. In this step, the degree of freedom will be adjusted using the approximation of Kenward and Roger. On the basis of this model, the estimated difference between the duloxetine and placebo groups at week 6 of administration, and its 95% confidence interval, and the p-value, will be calculated.

Examples of SAS codes for applying the above model are shown below.

```
proc mixed data=CDRSR order=internal;
  class SUBJID TRT VISIT AGEGR;
  model CHG=CDRSR_BASE AGEGR TRT VISIT TRT*VISIT / ddfm=kr;
```

```

repeated VISIT / type=un subject=SUBJID;
lsmeans TRT*VISIT;
estimate 'DLX vs PLB' TRT 1 -1 TRT*VISIT 0 0 0 0 1 0 0 0 0 -1 / cl;
run;

```

SUBJID: Subject identification number  
TRT: Group (DLX = duloxetine group; PLB = placebo group)  
VISIT: Stipulated observation time-points (Visits 3, 4, 5, 7 and 8)  
AGEGR: Age category (<12, ≥12)  
CDRSR\_BASE: CDRS-R total score baseline value  
CHG: Change in CDRS-R total score from baseline

If the above model does not converge, a covariance structure will be selected in the following order, and the MMRM method will be applied: (i) heterogeneous AR (1); and (ii) heterogeneous compound symmetry. In addition, time-course graphs of adjusted mean ( $\pm$  standard error) of change in total CERS-R score, estimated by the MMRM method, will be prepared for each treatment group.

### 9.1.2 Secondary analysis of primary endpoint

1) Analysis of the PPS by the MMRM method

Change in CDRS-R total score will be analyzed with the PPS, in the same manner as the primary analysis.

2) Analysis of change at week 6 of administration (analysis of covariance)

A) An analysis of covariance will be performed with change in CDRS-R total score from baseline to week 6 of administration as the response variable; treatment group as the fixed effect; and baseline CDRS-R total score, and age (<12, ≥12) as covariates. The estimated inter-group difference and 95% confidence interval, and p-value, will thus be calculated. If the CDRS-R total score at week 6 of administration is not available, the missing data will be imputed by the LOCF method.

B) On the basis of missing data imputation by the BOCF method, analysis of covariance will be performed in the same manner as above.

C) Likewise, analysis of covariance will be performed on the basis of missing data imputation by the modified BOCF method.

3) Supplemental analysis of missing data imputation methods:

With respect to change in CDRS-R total score, with multiple imputation with missing at random hypothesized, solely in the case of the duloxetine group the k-multiple of the inter-group difference ( $k = 0.1, 0.2, \dots$ ) for the treatment-group primary effect in the primary analysis MMRM method will be subtracted from the data obtained by missing data imputation, and analysis will be performed in a similar manner to the primary analysis. Despite differences in the time from baseline to the point at which data are missing, the subtracted values will be set the same. In the case of multiple imputation, taking the imputation to be performed 100 times, the seed value is set at 3,631. With respect to the analysis results (adjusted mean inter-group difference and standard error) with

imputation performed this number of times, these will be integrated as single results using proc mianalyze.

If the upper limit of the 95% confidence interval for adjusted mean inter-group difference is below 0, the k-value that overturns the results of the primary analysis is above 0, and this is taken to be the tipping point. The results of the primary analysis with the tipping point and the k-value up to reaching the tipping point will be reported. On the other hand, if the upper limit of the 95% confidence interval for adjusted mean inter-group difference in the primary analysis is above 0, a similar analysis is performed, but with a k-value below 0 taken to be the tipping point.

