8.1 Statistical analysis methods

The sponsor will commission a contract organization to perform the statistical analysis. The details of the analysis will be stipulated in the “Statistical analysis plan”, which will be prepared on the basis of this section. When any change is made to the analysis planned in the protocol, reason for a change will be specified in the statistical analysis plan without fail. Statistical analysis plan will be fixed prior to unblinding of data.

Number of subjects, arithmetic mean, standard deviation, minimum, median, and maximum will be calculated as summary statistics for the items measured by continuous data in principle. Number of subjects and proportion of each category will be calculated as summary statistics for the items measured by discrete value.

Level of significance at 0.05 (two-sided) will be used for all statistical tests unless otherwise specified. The primary endpoint in this study will be only change in CDRS-R total score from the baseline, so there will be no multiplicity adjustment for the statistical tests.

Subjects’ data will be shown in separate tables for each subject. Table will be tabulated for each group as a rule and a list of data of each subject will be shown by group and subject. SAS of Version 9.2 or higher will be used for all analyses and for creation of tables.

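### The tipping-point rule in SAP 9.1.2 takes its search direction from the upper confidence limit alone, so it fails when the estimate is zero or favours placebo

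*SAP*

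**What the plan says.** Protocol 8.10.3 promises a tipping-point analysis based on multiple imputation, because CDRS-R totals might be missing not at random. It gives no detail.

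SAP 9.1.2, item 3) supplies the rule:

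- Data are first imputed under missing at random. Then, "solely in the case of the duloxetine group the k-multiple of the inter-group difference" "for the treatment-group primary effect in the primary analysis MMRM method" "will be subtracted from the data obtained by missing data imputation". The list of k values starts at 0.1, rises in steps of 0.1 and has no stated end.
- Whenever the data went missing, "the subtracted values will be set the same".
- If the upper 95% limit in the primary analysis "is below 0, the k-value that overturns the results of the primary analysis is above 0".
- If the upper limit is above 0, "a similar analysis is performed, but with a k-value below 0 taken to be the tipping point".

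The example code in SAP 9.1.1 fixes the direction of the contrast as duloxetine minus placebo: "estimate 'DLX vs PLB' TRT 1 -1". A negative value therefore favours duloxetine.

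**The concern.** The shift given to an imputed duloxetine value is −k·D, so its direction depends on the signs of both k and D. The SAP fixes the sign of k from the upper confidence limit and never consults the sign of D. An upper limit above 0 is compatible with D on either side of zero, and the prescribed negative k improves duloxetine only if D is negative.

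The step size is 0.1·|D|. It shrinks with the estimate and is zero at D = 0. The SAP gives no bound on k and no fallback.

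A pre-specified sensitivity rule should be executable for any result the trial can give. If it is not, the analyst must devise a replacement after unblinding, and pre-specification exists to prevent that. An estimate favouring placebo is a realistic case: Protocol 8.2 reports −1.95 (placebo minus drug) in the HMCK study, which is D = +1.95 in the SAP's direction.

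**Working it through.** **Inputs.** Planned difference 5.9 (placebo minus duloxetine, so D = −5.9), SD 12.0, 66 evaluable per group and 10% dropout, all from Protocol 8.2 and SAP 4.3. Test level from Protocol 8.1: "Level of significance at 0.05 (two-sided) will be used for all statistical tests unless otherwise specified". Assumption: the share f of week-6 duloxetine values that are imputed equals the dropout rate, 10%, with 5% to 20% as a range.

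**The plan's own figure.** The effect size is 5.9/12.0 = 0.49. Exact t-test power is 0.794 with 65 per group and 0.8005 with 66, so 66 is reproduced. 66/0.9 = 73.3, rounded up to 74 per group, or 148 in total. The SAP states no numeric tipping point.

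**Sign convention.** Protocol 8.2 and SAP 4.3 quote differences as placebo minus drug, so the opposite reading of D needs checking. Under it, an upper limit below 0 would mean that duloxetine was worse, and the first branch of the rule would make no sense. Duloxetine minus placebo is the only reading that fits both the code and that branch.

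**Algebra.** Shifting a fraction f of duloxetine values by −k·D, with the standard error held fixed, gives

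- SE = 12·√(2/66) = 2.09, and 1.96·SE = 4.09
- difference(k) = D·(1 − f·k)
- upper limit U(k) = D·(1 − f·k) + 4.09
- crossing at k* = (D + 4.09)/(f·D), a shift of −k*·D points

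Results with f = 10%:

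| D | U at k = 0 | Sign of k searched | k at crossing | Shift at crossing (points) |
|---|---|---|---|---|
| −5.9 | −1.81 | positive | +3.1 | +18.1 |
| −2 | 2.09 | negative | −10.5 | −20.9 |
| −0.1 | 3.99 | negative | −399 | −39.9 |
| 0 | 4.09 | negative | none | −40.9 |
| +1.95 | 6.04 | negative | +31.0 | −60.4 |

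The first two rows behave as intended. At D = −0.1 each step moves U by 0.001, so about 3,994 steps are needed. At D = 0 every k leaves the data unchanged. At D = +1.95 each step of −0.1 raises U by 0.0195, so U(−5) = 7.02, and the only crossing has the sign that is not searched.

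**Sensitivity to f.** For f from 5% to 20%, the D = +1.95 crossing lies between k = +62.0 and k = +15.5, always positive. The D = −0.1 crossing needs 7,988 down to 1,997 steps.

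**Simulation check.** This used a week-6 ANCOVA with 74 per arm, 8 missing per arm, 100 imputations and Rubin's rules.

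- D = +2: U rises from 6.38 (k = 0) to 7.52 (k = −5) and 8.77 (k = −10).
- D = −2: U falls from 1.58 to −0.29 at k = −10.
- D = −0.1: U moves only from 3.66 to 3.44 at k = −20.

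The directions agree with the algebra. Large shifts also widen the interval: at D = +2, U is still 0.58 at k = +40. The fixed-SE crossings for large shifts are therefore approximate and tend to be too small; their signs do not change.

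**The case against.** The strongest reply is that the rule works where it bears on a claim of efficacy. If duloxetine wins, D is negative and positive k worsens its imputed values. Outright failure needs D at or above 0, when superiority has already not been shown. With SE 2.09, the chance of D above 0 is about 0.2% at the planned effect (5.9/2.09 = 2.82). It is about 2% with the HMCL difference of 4.66 and the pooled SD of 13.2 (4.66/2.30 = 2.03), about 17% if the true D is −2, and 50% under no effect. This stands. It limits the consequence, but the second branch was written for non-significant results and does not cover all of them.

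A reader might infer more than the documents support:

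- *That robustness cannot be judged because k has no units.* SAP 9.1.1 requires D to be reported and SAP 9.1.2 requires k, so k·D gives CDRS-R points. In a significant trial |D| is at least about 4.09, so a step is at least 0.41 points and k = 2 at least 8.2. Scaling by the estimated effect is a legitimate choice.
- *That the rule returns a false tipping point.* With D above 0 and k negative the upper limit never crosses 0, so the rule returns nothing. A large negative k can lift the lower limit above 0 (1.15 at k = −20 in the D = +2 simulation), but the SAP's rule is stated on the upper limit.
- *That nothing else departs from missing at random.* The BOCF and modified BOCF analyses in SAP 9.1.2 do, as does counting withdrawn subjects as non-responders in SAP 9.2.1. They do not vary the size of the departure, so they cannot supply a tipping point.

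It is also fair that a fixed-point shift may find no plausible crossing. At D = +1.95 it needs about −60 points, whereas a subject entering at the minimum total of 40 can fall only 23 before reaching the floor of 17. Reporting that none exists within a stated range is still a defined answer, which the present rule does not give.

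**Conclusion.** The concern holds as a defect of the supplemental tipping-point analysis only. When D is above 0, the stated search moves away from the upper-limit crossing; this follows from the signs alone and needs no numerical assumption. When D is exactly 0 there is no shift. When D is small and negative, a crossing exists in principle but is impractically far off (about 4,000 steps at D = −0.1). The sizes rest on SD 12.0, 66 per group, a fixed SE and an assumed 10% imputed.

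The rule is sound when D is clearly negative, and the primary MMRM test and the sample size are untouched. The point still merits correction, because a stated rule points the wrong way for a result that one of the two reference studies produced, in the one analysis that the protocol labels as addressing data missing not at random.

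**What to change.** In SAP 9.1.2, item 3), set the direction of the shift without reference to the sign of D. If the primary result is significant in favour of duloxetine, worsen its imputed values; otherwise improve them.

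The simplest form is a shift in fixed CDRS-R points, for example in 1-point steps, over a range stated in advance and bounded by the scale. Totals run from 17 to 113, so 96 points is the outer limit; the 23 points available to a subject entering at 40 is a stricter bound for improvement. Report the shift at which the upper 95% limit crosses 0, or that none exists within the range. At D = −0.1 and 10% imputed this takes about 40 steps instead of about 3,994. It also removes the doubt over whether D means the week-6 contrast or an average over visits.

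At minimum, keep multiples but use |D| with the direction rule above, and state a fallback unit for D near 0, such as the planned 5.9.

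The cost is a few words in the SAP before the key break and one changed macro parameter. No further data are needed and the primary analysis does not change.
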